#### **9.2.2.1 SPEP, UPEP, SFLC, SIFE, and UIFE**

Serum protein electrophoresis, UPEP, SIFE, UIFE, and SFLC will all be conducted at the central laboratory. Samples will be collected every  $28 \pm 7$  days (starting from cycle 1 day 1) irrespective of cycle duration including dose delays and treatment discontinuation. Blood will be obtained for SFLC, SPEP, and SIFE. Twenty-four-hour urine samples will be obtained for UPEP and UIFE. A 24-hour urine sample obtained as standard of care may be used as the screening assessment, if obtained within 24-hours prior to signing consent and sent to central lab for analysis. Results for SPEP, UPEP, or SFLC must be available at screening and before randomization. Serum protein electrophoresis, UPEP, and SFLC will be repeated on cycle 1 day 1 (unless screening values are within 14 days of cycle 1 day 1).

Post cycle 1 day 1, UPEP and UIFE will be collected every 28 days as part of every myeloma disease assessment, along with SPEP, SIFE, and SFLC, and submitted to the central laboratory for processing.

Subjects will be evaluated for disease response and progression according to the IMWG response criteria in Section 12.11. Disease status categories include sCR, CR, VGPR, PR, SD, and PD. Investigator evaluation of disease response is to be based solely on the central laboratory results, not on local laboratory results for laboratory-based parameters.

The following confirmation assessments are required for all response categories (sCR, CR, VGPR, and PR; refer to definitions in Section 12.11):

- all response categories require 2 consecutive assessments before initiation of any new therapy
- all categories also require no known evidence of progression including new bone lesions if radiographic studies were performed
- confirmation of CR or better requires bone marrow assessment (aspirate or biopsy per IMWG-URC guidelines; sCR determination in this study requires a bone marrow biopsy or aspirate clot for immunohistochemistry)
- extramedullary plasmacytoma evaluation (if present at screening)

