#### **10.2.1.3 Per-Protocol Population**

The per-protocol population will include all randomized subjects who do not have any major protocol deviations that might affect the interpretation of the analyses of the efficacy endpoints. The major protocol deviations include:

- Major inclusion criteria not met
- Major exclusion criteria not met
- Major treatment non-compliance
  - Treatment received different from treatment randomized
  - Concomitant use of protocol prohibited medications.

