MRD[-] rate at 12 months is defined as the proportion of subjects with achievement of MRD negativity at 12 months (\pm 4 weeks) from randomization, as assessed by NGS method at a 10^{-5} threshold among all ITT subjects. Per protocol, the 12-month sample may be omitted if the MRD analysis with confirmed results was performed within 4 months prior to the scheduled test at 12 months from randomization, or if subject has started new antimyeloma therapy prior to 12-month landmark, or if disease progression is recorded. So, MRD negativity results from bone marrow samples obtained at 8 to 13 months from randomization and prior to new antimyeloma therapy or disease progression will be considered in the calculation.

Overall Response Rate (ORR)

ORR is the proportion of ITT subjects whose best overall response is sCR, CR, VGPR, or PR per IMWG-URC over the duration of the study.

Overall Survival (OS)

OS is defined as the time (in months) from randomization to the date of death due to any cause.

$$\text{OS} = (\text{death date or censoring date} - \text{randomization date} + 1) / 30.4$$

Subjects still alive or lost to follow-up or withdrawn consent from study by the analysis time will be censored at the date on which the subject is last known to be alive.

Progression-Free Survival (PFS)

PFS will be calculated from the date of randomization until the first documentation of PD or death due to any cause, whichever occurs first.

$$\text{PFS (month)} = (\text{PD/death date or censoring date} - \text{randomization date} + 1) / 30.4$$

The duration of PFS will be right censored for subjects who meet any one of the following conditions: (1) no baseline/no post-baseline disease assessments; (2) starting a new anti-myeloma therapy before documentation of progressive disease or death; (3) progressive disease or death immediately after more than 1 consecutively missed disease assessment visit (that is, progressive disease or death immediately after more than **63** days without disease assessment visit); (4) alive without documentation of disease progression before the analysis trigger date; (5) lost to follow-up or withdrawn consent. These censoring rules for PFS primary analysis are **following the derivations used for historical ASPIRE study.**

Table 5-1. Censoring Rules for Primary PFS Analysis

Situation	Date of Progression or Censoring	Outcome
No baseline/no post-baseline disease assessments	Date of randomization	Censored

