Prior or concomitant therapy (218 - 222, 228 in protocol):

- Immunotherapy, monoclonal antibody therapy or approved anti-cancer chemotherapy within 28 days prior to randomization (218, 219, 220)
- Glucocorticoid therapy exceeding a cumulative dose of 160mg within 14 days prior to randomization (221)
- Focal radiation therapy within 7 days prior to randomization, radiation to large marrow reserves within 28 days (i.e., prior radiation must have been to <30% of the bone marrow) (222)
- Currently receiving treatment in another investigational device or drug study within 28 days of randomization (228)

Organ Function Assessment:

- Calculated or measured creatinine clearance < 30 mL/min (calculation must be based on the Cockcroft and Gault formula) within 28 days prior to randomization (244)
- Major treatment non-compliance
 - Treatment received different from treatment randomized (IPD Criteria 500).
 - Incorrect carfilzomib dose: under-dosing that meets IPD Criteria 502.
 - Failure to obtain extramedullary plasmacytoma assessment and /or bone lesion assessment as part of baseline disease assessment such that the primary endpoint cannot be assessed (IPD Criteria 801).
 - Any C1D1 disease assessment or disease specific lab required at baseline is missed or collected in such a way that patient is not measurable as defined per protocol (IPD Criteria 802).
 - Failure to obtain 2 consecutive disease response assessments that may impact the assessment of the primary endpoint (IPD Criteria 803).

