7.3 Final Analysis

The final analysis will be performed after all subjects have completed the study. Final analysis will be based on a clean database lock.

The hypotheses for the primary and key secondary objectives (ORR, PFS, and convenience after cycle 4 of treatment) will be tested using a fixed sequence hierarchical

testing procedure to control the family-wise type I error rate at 1-sided 0.025 level. The testing is ordered as follows: non-inferiority of ORR, non-inferiority of PFS, and superiority of patient-reported convenience after cycle 4 of treatment.

Starting with the hypothesis of ORR, if any null hypothesis in the sequence is rejected at a 1-sided significance level of 0.025, then the subsequent null hypothesis will be tested. Otherwise, if any null hypothesis failed to be rejected, then the subsequent hypotheses will not be tested.

For the primary endpoint, the stopping boundary is 0.025 in p-value scale in the final analysis.

The final analysis of efficacy endpoints will be based on the ITT analysis set, while the final analysis of safety endpoints will be based on the safety analysis set. Sensitivity analyses of efficacy endpoints based on the per protocol set might be performed only if the PP population was less than 90% of the ITT population.

8. Data Screening and Acceptance

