8.3 Handling of Missing and Incomplete Data

The descriptive statistics will identify the extent of missing data. Rules for handling missing data related to endpoints are described in the endpoint definitions or in the description of analyses. The handling of incomplete and partial dates for adverse events,

concomitant medications, new antimyeloma therapy, death, prior multiple myeloma therapy, and relapse/progression to prior multiple myeloma therapy are described in [Appendix A](#).

The calculation of scores and methods to deal with missing data will be handled according to the EORTC QLQ-C30 questionnaire's standard scoring guidelines.

No imputation will be done for the analysis of the primary and key secondary endpoints. The frequency of missing disease assessments and deviation of the actual disease assessment times from the scheduled assessment times will be summarized by treatment arms. Sensitivity analyses will be performed to assess the impact of missing any disease or response assessment on the analysis of ORR and PFS (i.e., analysis in Per Protocol Set). Similar analysis will be performed for QOL endpoints.

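### For ORR, the only check SAP 8.3 names for missed response assessments is a conditional per-protocol analysis that excludes subjects lacking two consecutive assessments, so it cannot test how far the non-inferiority result depends on their unknown outcomes

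*SAP*

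**What the plan says.** - **Confirmation.** Protocol 9.2.2.1: "all response categories require 2 consecutive assessments before initiation of any new therapy". Protocol Appendix 11 repeats this and adds that a confirmed category is not later downgraded.
- **Endpoint.** SAP Section 5: "ORR is the proportion of ITT subjects whose best overall response is sCR, CR, VGPR, or PR per IMWG-URC". SAP 8.3: "No imputation will be done for the analysis of the primary and key secondary endpoints". A subject without a confirmed response stays in the ITT denominator as a non-responder.
- **Per-protocol set.** SAP 6.3 lists, under major treatment non-compliance, "Failure to obtain 2 consecutive disease response assessments that may impact the assessment of the primary endpoint (IPD Criteria 803". It also excludes subjects for eligibility deviations, wrong treatment, under-dosing and missing baseline assessments.
- **Check for missed assessments.** SAP 8.3 promises sensitivity analyses of "the impact of missing any disease or response assessment on the analysis of ORR and PFS (i.e., analysis in Per Protocol Set". It also summarises the frequency of missed assessments by arm.
- **Condition.** SAP 7.3 says per-protocol sensitivity analyses "might be performed only if the PP population was less than 90% of the ITT population".
- **Other ORR sensitivity analyses.** SAP Table 9-1 and SAP 9.5.1 list investigator assessment, the computer algorithm (ORCA), unstratified, per-protocol and the COVID-19-adjusted set (mFAS).

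**The concern.** A check on missing outcomes should ask what happens to the conclusion if the unknown outcomes differ from what the primary analysis assumes. Here the primary analysis takes them all as non-response, in both arms. The named check does not vary that assumption. It deletes the subjects to whom the assumption applies.

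In a non-inferiority trial, counting unknown outcomes as failures in both arms is not automatically conservative. If some of the unassessed twice-weekly (BIW) subjects had in fact responded, the ITT analysis understates the reference arm and makes the once-weekly (QW) arm look closer to it than it is. None of the listed ORR analyses would show at what point that changes the result. The 90% condition also means the named check may not be run.

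**Working it through.** **Inputs.** From SAP 3.2 and 9.5.1: retention r = 0.6; historical log risk ratio U_h = ln 0.755 with SE_h = 0.041; 1-sided level 0.025; 460 subjects randomised 1:1, so 230 per arm; assumed ORR 86.6% in both arms. The historical CI 0.696 to 0.818 gives SE_h = (ln 0.818 − ln 0.696)/(2 × 1.96) = 0.0412, which agrees. The numbers of IPD 803 subjects are assumptions.

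**Statistic (SAP 9.5.1).**
z = [ln RR − 0.4 ln 0.755] / √(SE_n² + (0.4 × 0.041)²)
with SE_n² = (1 − p₁)/(p₁n₁) + (1 − p₂)/(p₂n₂), 0.4 ln 0.755 = −0.1124 and (0.4 × 0.041)² = 0.000269. This is the unstratified variance; the SAP uses the stratified estimate.

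**The plan's own figure.** At 86.6% in both arms and 230 per arm, power is 79.9% without the futility look and 78.3% to 78.5% with it, against the stated 80%. The statistic is the one the plan uses.

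**Illustration: 10 IPD 803 subjects per arm, 86.6% response among the other 220.** Responders per arm: 0.866 × 220 = 190.52.

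| Analysis | QW | BIW | RR | SE | z | 1-sided p |
|---|---|---|---|---|---|---|
| ITT as planned | 190.52/230 = 82.8% | 190.52/230 = 82.8% | 1.000 | 0.0455 | 2.470 | 0.007 |
| Per-protocol (803 exclusions only) | 190.52/220 = 86.6% | 190.52/220 = 86.6% | 1.000 | 0.0409 | 2.746 | 0.003 |
| ITT, 5 of the BIW ten respond, no QW | 82.8% | 195.52/230 = 85.0% | 0.974 | 0.0440 | 1.966 | 0.0247 |
| ITT, 6 of the BIW ten respond, no QW | 82.8% | 196.52/230 = 85.4% | 0.969 | 0.0437 | 1.862 | 0.031 |
| ITT, all BIW ten respond, no QW | 82.8% | 200.52/230 = 87.2% | 0.950 | 0.0425 | 1.440 | 0.075 |

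For the last row: ln 0.950 = −0.0512, so z = (−0.0512 + 0.1124)/0.0425 = 1.44. In this example the conclusion tips between 5 and 6 BIW responders. The two planned rows both pass comfortably and give no hint of this.

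**Would the per-protocol analysis be run?** Ten per arm leaves 440/460 = 95.7%. On IPD 803 exclusions alone the 90% condition is not met. It takes more than 0.10 × 460 = 46 exclusions of all kinds.

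**Direction of the per-protocol result.** It depends on which arm has more missed assessments:

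| IPD 803 subjects (QW/BIW) | Response among the rest (QW/BIW) | ITT | Per-protocol |
|---|---|---|---|
| 10/0 | 86.6%/86.6% | RR 0.957, p = 0.057 | RR 1.000, p = 0.003 |
| 0/10 | 82%/86.6% | RR 0.990, p = 0.013 | RR 0.947, p = 0.094 |

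In the first case the per-protocol set is the more lenient analysis, in the second the stricter one.

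**The case against.** The strongest reply is that ITT alone decides non-inferiority and already carries unconfirmed subjects as non-responders. If the QW arm has the excess of missed assessments, ITT bears the loss and a favourable per-protocol result cannot rescue it. Missed assessments are tabulated by arm (SAP 8.3), as are important protocol deviations by category (SAP 9.3). All of this stands. A reader might infer that the plan hides missed assessments from the primary conclusion, and the documents do not support that. What remains is that frequency tables show how often outcomes are unknown, not whether they could change the result.

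A reader might also infer the following, none of which is established:

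- **That the per-protocol set removes only failures.** Its other exclusions can remove responders. Even under IPD 803, the wording is that the gap may affect the endpoint, the full deviation list is a separate study document, and Protocol Appendix 11 lets the two samples be drawn on the same day. A confirmed PR with an unconfirmed upgrade might also be coded. Hence generally, not always, a non-responder.
- **That early toxicity in the QW arm feeds IPD 803.** Assessments continue after treatment stops (Protocol 9.2.2). Death, progression, withdrawal and new therapy end the required assessments, so a gap after them need not be a deviation.
- **That adding IPD 803 is an undeclared change from the protocol.** Protocol 10.2.1.3 lists items such as "Treatment received different from treatment randomized", but introduces them as what major deviations include, and Protocol 10.2.4 leaves missing-data detail to the SAP.
- **That the same argument covers PFS.** It rests on confirmation of response. For PFS, SAP 9.5.2 also plans interval-censored and scheduled-date analyses.

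**Conclusion.** The point holds for ORR in a limited form. The one check named for missed response assessments excludes the subjects in question, might not be run, and cannot test the result against their unknown outcomes; no other listed ORR analysis fills the gap. The primary analysis, its type I error and the sample size are not called into question.

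The direction of any per-protocol bias is unknown in advance, so the documents do not support saying that the check favours the QW arm.

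The size rests on assumed counts. With 10 unassessed subjects per arm, moving from non-response in both arms to the extreme unfavourable to QW takes RR from 1.00 (p = 0.007) to 0.95 (p about 0.075). With very few such subjects the gap would have little effect.

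**What to change.** In SAP 8.3, for ORR, replace the parenthesis that equates the check with the per-protocol analysis by an ITT tipping-point analysis, run regardless of the 90% rule in SAP 7.3. For subjects lacking two consecutive assessments, vary the assumed response by arm, from non-responder in both arms to non-responder in QW and responder in BIW. Report where the synthesis p-value crosses 0.025.

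IPD 803 may stay in the per-protocol definition. Deleting it would make that set treat these subjects exactly as ITT does, and would lose the contrast that is informative when BIW has more missed assessments.

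The cost is SAP wording and one extra table. Data collection, sample size and the primary analysis do not change.

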6.4 Pharmacokinetic/Pharmacodynamic (PK/PDn) Analyses Set(s)

The PK Analysis Set will include all subjects who have received at least 1 dose of carfilzomib and 1 post-dose PK sample collected, as defined by the Schedule of Assessments. The PDn Analysis Set will include a subset of subjects in the PK Analysis set who have consented to participate in the optional PK/PDn substudy. These subjects will be evaluated for pharmacokinetics and pharmacodynamics unless significant

protocol deviations affect data analysis or if key dosing, dosing interruption, or sampling information is missing.

6.5 Interim Analyses Set

The interim analysis set for interim futility analysis include the first 230 subjects (50% of the planned total 460 subjects) who have been randomized and had the opportunity to be followed for a BOR assessment by the date when treatment was completed, confirmed PD or death occurred, subject was lost to follow-up, withdrew consent, or started new antimyeloma therapy, whichever occurred first.

6.6 Modified Full Analysis Set

The modified full analysis set (mFAS) will be used in the sensitivity analysis for primary endpoint and key secondary endpoints in order to adjust for the COVID-19 impact on the ITT population. The mFAS is a subset of ITT Analysis Set excluding subjects who are impacted by COVID-19.

The COVID-19 impact refers to:

- (1) any COVID-19 adverse events which are identified using the COVID-19 Standardized MedDRA Query (SMQ) narrow search strategy, and COVID-19 events collected on the Confirmed COVID-19 Status CRF;
- (2) the reason for Investigational Product (IP)/Non-IP Dose Change/Withheld/Dose Delay is COVID-19 control measures recorded on the CRFs for IP Administration and Non-IP Administration;
- (3) the reason for ending IP/Non-IP is COVID-19 control measures recorded on CRFs for End of IP Administration and End of Non-IP Administration;
- (4) IPDs related to COVID-19 control measures;
- (5) COVID-19 related protocol deviation: 940 series, 950 series and 960 series of protocol deviation codes in the study IPD list.

7. Planned Analyses

7.1 Interim Analysis and Early Stopping Guidelines

An Independent Biostatistics Group (IBG) will perform the interim analyses and provide the interim report to an independent Data Monitoring Committee (DMC). The initial assessment from this committee will be planned after 30 subjects (approximately 15 for the experimental arm and 15 for the control arm) have been enrolled and have finished the first cycle of treatment to ensure safety of all arms. Thereafter, the DMC will review

all available safety/efficacy data periodically (approximately every 6 months) and evaluate the efficacy analysis once for the non-binding interim analysis for futility. The primary purpose of the interim futility analysis is to assess the futility in terms of ORR. The non-binding interim futility analysis is planned to occur when the first 230 subjects (50% of the planned total 460 subjects) have been randomized and had the opportunity to be followed for a best overall response (BOR) assessment by the date when treatment was completed, confirmed PD or death occurred, subject was lost to follow-up, withdrew consent, or started new antimyeloma therapy, whichever occurred first. Using an O'Brien-Fleming type beta-spending function, the stopping boundary for futility in p-value scale is 0.289. The study is futile in terms of ORR if the observed p-value > 0.289. With such a stopping boundary, the trial has over 70% probability to stop for futility when the null hypothesis of inferiority is true.

The IBG and DMC will have access to subjects' individual treatment assignments. To minimize the potential introduction of bias to the conduct of the study, members of the DMC and IBG will not have any direct contact with study center personnel or subjects. The DMC will communicate major safety concerns and recommendations regarding study modification or termination based on the safety data and interim futility stopping criteria to Amgen in accordance with the DMC charter.

Records of all meetings will be maintained by the DMC for the duration of the study. Records of all meetings will be transferred and stored in the TMF (in accordance with SOP-427356) at the conclusion of the study.

Further details are provided in the DMC charter.

Data will be subject to ongoing checks for integrity, completeness, and accuracy in accordance with the Data Management Plan with the expectation that all outstanding data issues are resolved ahead of the snapshot. The data will be locked to prevent further changes, and a snapshot of the locked database will be used in the analysis.

7.2 Primary Analysis

The primary analysis corresponds to the final analysis.

7.3 Final Analysis

The final analysis will be performed after all subjects have completed the study. Final analysis will be based on a clean database lock.

The hypotheses for the primary and key secondary objectives (ORR, PFS, and convenience after cycle 4 of treatment) will be tested using a fixed sequence hierarchical

testing procedure to control the family-wise type I error rate at 1-sided 0.025 level. The testing is ordered as follows: non-inferiority of ORR, non-inferiority of PFS, and superiority of patient-reported convenience after cycle 4 of treatment.

Starting with the hypothesis of ORR, if any null hypothesis in the sequence is rejected at a 1-sided significance level of 0.025, then the subsequent null hypothesis will be tested. Otherwise, if any null hypothesis failed to be rejected, then the subsequent hypotheses will not be tested.

For the primary endpoint, the stopping boundary is 0.025 in p-value scale in the final analysis.

The final analysis of efficacy endpoints will be based on the ITT analysis set, while the final analysis of safety endpoints will be based on the safety analysis set. Sensitivity analyses of efficacy endpoints based on the per protocol set might be performed only if the PP population was less than 90% of the ITT population.

8. Data Screening and Acceptance

8.1 General Principles

The objective of the data screening is to assess the quantity, quality, and statistical characteristics of the data relative to the requirements of the planned analyses. The database will be subject to edit checks outlined in the data management plan by Amgen Clinical Data Management (CDM) department. Data inconsistencies and suspicious values will be reviewed and resolved before the database is locked.

